
The goal of this study is to more fully evaluate the rapid onset of night-time itch and scratch relief following treatment with Crisaborole in comparison to vehicle treatment in children with AD. Moreover, this study will assess the QoL and sleep within the associated caregivers.

Significance

Itch, night-time scratch and sleep are key symptoms experienced by patients with AD and impact not only the patient but the families of the patients with AD, particularly for young age children. Therefore, more fully understanding the cessation of the feeling of itch, action of scratch and improvements in sleep following treatment of Crisaborole (2% BID) would provide additional insight to the treatment profile. This study will specifically evaluate the rapid onset of itch and night-time scratch relief, improvement in sleep (both in the participant and their primary caregiver) and improvement in AD-inflammatory markers following crisaborole therapy twice daily (2% BID) in children 3 months to \leq 11 years old.

This study will also provide critical understanding of the ability of the accelerometry/actigraphy devices to measure drug-induced changes in scratching, movement and sleep quantity in children with symptomatic AD and quality of life in caregivers. It will also provide a physiological comparator for PRO/ObsRO assessments and ultimately enhance understanding of AD.

SCHEDULE OF ACTIVITIES

Period/Visit	Screening	V01 (Baseline)	V02	V03	V04	V05
Day	-28 to -7	-7	1	2	8	15
Window(days)	NA	+/- 3	+/- 3	+ 0.5	+/- 3	+/- 3
ENROLLMENT PROCEDURES						
Informed consent / assent	X	X				
Demographics, medical history including AD history/treatment	X	X				
Inclusion and exclusion criteria Review (both child and caregiver)	X					
Inclusion and exclusion criteria ‡ (both child and caregiver)		X				
Pregnancy test for female caregivers of child-bearing potential		X				
Wide Range Achievement Test 4 (WRAT-4; caregivers only)		X				
MEDICAL PROCEDURES						
Vital signs		X				
Height and weight		X				
ASSESSMENTS						
Investigator's Static Global Assessment (ISGA) (both child and caregiver at V01, only child thereafter)		X	X		X	X
Eczema Area and Severity Index (EASI)		X	X		X	X
% Body Surface Area (BSA)		X	X		X	X
Childhood Asthma Control Test (ages 4 to ≤ 11 years)		X				
Tape Stripping (Biomarker Assessment)**		X		X		X
PATIENT REPORTED/OBSERVER-REPORTED OUTCOMES (PROs/ObsROs)						

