4.1. Inclusion Criteria

Both child and caregiver participants must meet all of the following inclusion criteria to be eligible for enrollment into the study:

Children (3 months to ≤ 11 years)

1. Male or female participants aged between ≥ 3 months of age and ≤ 11 years of age at Day -7.
2. Written informed consent from participant/parent(s)/guardian(s).
3. Native English or demonstrated fluency in English (as age appropriate).
4. Participants and parent(s)/guardian(s) are willing and able to comply with study instructions, study visits, procedures, and device placement (devices will be optional for those who have active AD on location of device placement, with a minimum of at least one wrist device needed for enrollment).
5. Have a clinical diagnosis of AD according to the criteria of Hanifin and Rajka.
6. Have AD involvement $\geq 5\%$ Treatable % Body Surface Area (BSA) excluding the scalp and less than 40% BSA.
7. Have an ISGA score of Mild (2) or Moderate (3) at the baseline visit.
8. Have an EASI total score of ≥ 3 at Day -7.
9. Have a minimum Observer Reported Itch Assessment score of 2 at Day -7 (ages 3 months - ≤ 5 years only) or a minimum Patient Reported Itch Severity Scale score of 2 (ages 6 years - ≤ 11 years old) at Day -7.
10. Participant/parent(s)/guardian(s) agrees to refrain from applying diaper rash creams, lotions, ointments, powders, etc. where AD lesions are present, unless AD lesions are present where crisaborole cannot be applied (face within 1 or 2 fingers away from the mouth and hands/fingers).
11. Participants must agree to refrain from applying crisaborole/vehicle to AD lesions on the fingers or hands or within 1 or 2 fingers away from the the mouth to prevent inadvertent ingestion of ointment.

Adult Caregiver

1. Primary caregiver of the child participant, between ≥ 18 years of age and ≤ 75 years of age.
2. Able to understand and cooperate with study procedures and give informed consent.
3. Native English or demonstrated fluency in English.
4. Evidence of a personally signed and dated informed consent document indicating that the participant has been informed of all pertinent aspects of the study.
5. ISGA score of 0 or 1 of AD at the baseline visit, and no reported diagnosis of Atopic Dermatitis.
6. WRAT-4 Word Reading Subtest equivalent to 8th grade reading level or greater.

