5. STUDY PROCEDURES

The study will consist of a screening/baseline (in- laboratory) visit on Day -7 (V01), an in- laboratory visit Day 1 (V02), an in- laboratory visit on Day 2 (V03) for tape-stripping, and Day 8 (V04) for an assessment of the severity of the AD and a final in- laboratory visit on Day 15 (V05) for an assessment of the AD, tape-stripping, completion of ObsROs and return devices. Throughout the study, the participants and caregivers will wear accelerometry/actigraphy devices continuously (optional for those who have active AD on location of device placement, with a minimum of at least one wrist device needed for enrollment; devices may be removed for short periods of time for such things as the purposes of bathing, etc.). Enrolled participants will be randomly assigned to each arm of the study. Participants may come in for an unscheduled visit as needed (i.e., to replace compound, etc.). All in-person study activities, including informed consent and pregnancy testing, will be completed at the Laboratory for Human Neurobiology, [name]. All activities performed in the laboratory are accomplished in private rooms. Primary caregivers will be provided with ample time and a privacy curtain to change into a gown during assessment for exclusion of Atopic Dermatitis, and primary caregivers will accompany children during all activities to ensure participant privacy. All at-home study activities will be completed in the participants' home.

Phone Screening - Day-28 to -7 (~15 minutes):

- Verbal consent (including assent where applicable)
- Assign Participant ID (a sequentially assigned numerical ID used to identify participant on all study documents and in the electronic data capture [EDC] system)
- Screening demographics, medical history including AD history/treatment (includes, race, ethnicity, and gender)
- Eligibility screening (review of inclusion and exclusion criteria)

Baseline Visit 1 (V01)/Day -7 (+/- 3) – In Laboratory (~2 hours):

- Written Informed consent (including assent when applicable)
- Participants are randomly assigned to one of the two arms of the study
- Screening demographics (includes race, ethnicity, gender, and significant medical

history/treatment)

- Pregnancy test for female caregivers of child-bearing potential
- Wide Range Achievement Test 4 (WRAT-4)
- Eligibility Screening (Inclusion/Exclusion criteria)
- Vital signs
- Height and weight

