Visit 3 (V03)/ Day 2 (+/- 12 hours) – In Laboratory (~30 minutes):

1. Collect Tape Stripping
2. Weigh tube of compound or vehicle

Visit 4 (V04) / Day 8 (+/- 3 day) In Laboratory (~1 hour):

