1. ISGA
2. EASI
3. % affected BSA calculation
4. Children's Sleep Health Questionnaire (CSHQ; ages ≥ 4 to ≤ 11 years) OR BISQ (Brief Infant Sleep Questionnaire; ages 3 months - <4 years)
5. Medical Outcome Sleep Scale (MOS-Sleep; caregivers only)
6. Observer Global Impression of Change (OGIC)
7. Faces, Legs, Activity, Cry, and Consolability Scale (FLACC)
8. Dermatitis Family Impact Questionnaire (DFI; parent/guardian(s); ages 3 months - ≤ 11 years)
9. Children's Dermatology Life Quality Index (CDLQI; ages ≥ 4 - ≤ 11) OR Infants Dermatitis Quality Of Life Index (IDQOL; ages 3 months- <4 years)
10. Observer-Reported Patient-Oriented Eczema Measure (POEM; ages 3 months - ≤ 11 years)
11. In laboratory dose application training, including weight of the compound or vehicle tube
12. Retrieve and re-issue Accelerometry devices (Devices will be optional for child participants who have active AD on location of device placement, with a minimum of at least one wrist device needed for enrollment.)

Visit 5 (V05) / Day 15 (+/- 3 day) or Early Termination (ET)– In laboratory (~2 hours):

The primary purpose of this visit is to retrieve devices and complete end-of-study assessments. In addition, the following procedures will occur.

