1. ISGA
2. EASI
3. % affected BSA calculation
4. Tape Stripping
5. Observer Reported Itch assessment (ORIA; ages 3 months - ≤ 11 years)
6. Patient Reported Itch Severity Scale (ages 6 years to ≤ 11 years old)
7. Observer Global Impression of Severity (OGIS; ages 3 months - ≤ 11 years)
8. Peak Pruritis NRS (Caregivers)
9. Children's Sleep Health Questionnaire (CSHQ; ages ≥ 4 to ≤ 11 years) OR BISQ (Brief Infant Sleep Questionnaire; ages 3 months - <4 years)
10. Medical Outcome Sleep Scale (MOS-Sleep; caregivers only)
11. Observer Global Impression of Change (OGIC)
12. Device Comfort Questionnaire (DCQ) / Observer Device Comfort Questionnaire (ODCQ)
13. Faces, Legs, Activity, Cry, and Consolability Scale (FLACC)
14. Dermatitis Family Impact Questionnaire (DFI; parent/guardian(s); ages 3 months- ≤ 11 years)
15. Children's Dermatology Life Quality Index (CDLQI; ages ≥ 4 - ≤ 11) OR Infants Dermatitis Quality Of Life Index (IDQOL; ages 3 months- <4 years)
16. Observer-Reported Patient-Oriented Eczema Measure (POEM; ages 3 months - ≤ 11 years)
17. Coordinator to retrieve and track return of devices.
18. Weigh and return compound or vehicle tube
19. Record participant disposition (completed study, left study early and reasons)

Participant Withdrawal/Stopping Rules

Participant comfort with the proposed procedures will be regularly assessed and no procedure will continue if the participant expresses discomfort or a desire to stop for any reason. If one Unanticipated Problem (UP) occurs, the study will be suspended until the investigators determine, with the BUMC/BMC IRB's input, that sufficient corrective measures can be put into place to allow it to proceed.

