8.2 Safety Review

Safety review for this study will be accomplished throughout the study and monitor all study activities identified in the schedule of activities. Risks to be monitored include: hypersensitivity, application site pain, application site discomfort, skin irritation, pyrexia, upper respiratory tract infection, diarrhea, cough, and any unknown risks or unanticipated problem identified in the performance of the study. This will be accomplished by study staff personnel as part of each visit activity, spontaneously reported by the caregivers, and monitored for all participants enrolled throughout the study. Specifically during each study visit, study staff will assess the level of skin irritation and participant reported discomfort (or AD flare up) from both the wearing of devices and/or subsequent topical application of crisaborole/vehicle. The Principal Investigator will be notified of any AEs immediately. All other reporting plans are outlined in section 8.3.

Signs of AD (based on % BSA) will be measured and evaluated throughout the study period on laboratory visits 3, 4, and 5 (days 2, 8, 15) by the study dermatologist. Participants whose BSA exceeds 40% at visits 3 and 4, will be instructed to terminate the use of vehicle/crisaborole and will be withdrawn from the study. We will monitor collected BSA percentages at each time point and their change from baseline. Participants will also be provided with a 24/7 phone number should they need to contact the laboratory after hours.

Appropriate documentation of any and all identified unanticipated or adverse events will be properly reported to the IRB including appropriate mitigation and reports for recommended changes, with unanticipated problems within 7 days. A document listing any identified safety related events will be maintained and monitoring of this list will be ongoing throughout the study as a means to track and review these events (accomplished by comparative analysis of each event in comparison to all other events throughout the study) to determine expectedness, relatedness, or suggestion of new risks that may have been identified. Other events will be documented, assessed and monitored by staff and investigators and reported at the time of continuing review. Monthly reviews of blinded adverse events will be

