8.4 Research Related Injury

Possible social risks: These are extremely low in this study and pertain to the unintentional release of personal information.

Mitigation of social risks: To safeguard confidentiality and the privacy of protected information, each study participant will be assigned a unique code number. A separate file linking the participants' name with study number and identifiers will be kept in a password-protected data file, accessible only by the PI and the study coordinator. All study forms will be kept in secure locked file cabinets. The study investigators will assume full responsibility to maintain the confidentiality of all data. All study results will be presented only as statistical aggregates that will neither identify, nor permit identification of, individual participants.

Possible risk associated with digital health devices: The risks associated with these devices include physical discomfort if the participant is not used to wearing wrist accelerometers and/or ankle devices, and possible skin irritation or reaction, such as an AD flare-up in children with the skin condition. If the participant experiences skin irritation or notice signs of an AD flare-up in the area that the child wears the device(s), they will be instructed to remove the device(s) and notify the study team immediately.

Mitigation of risks associated with digital health devices: If the participant is unable to wear the device due to discomfort (or AD flare up) the participant will notify study staff and the Principal Investigator may allow the participant to continue the study without wearing the discomforting device or withdraw the

participant from the study. Devices will be optional for child participants who have active AD on location of device placement, with a minimum of at least one wrist device needed for enrollment.

Possible risk associated with tape stripping: Tape stripping is routinely performed and is considered a minimally invasive approach for identifying biomarkers for Atopic Dermatitis and is an acceptable alternative to traditional biopsies. The only minimal risk associated with tape stripping is mild discomfort and potentially superficial surface reddening of the skin at the location of the tape. This is typically reported after 50-60 tape stripplings. In this study we will only be doing ~20 tape stripplings per sample. Tape stripping sensation is similar to removal of a band-aid.

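### Section 8.2 ends follow-up as well as treatment when BSA exceeds 40%: a Day 8 trigger costs that child 7 of 14 ORIA analysis days, for a probably small number of children

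*Combined protocol and SAP*

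**What the plan says.** Section 8.2 sets a rule for worsening disease. Children whose BSA is above 40% at Visits 3 and 4 "will be instructed to terminate the use of vehicle/crisaborole and will be withdrawn from the study". Entry criterion 6 in Section 4.1 requires "less than 40% BSA", so the trigger sits at the entry ceiling.

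Section 8.2 says that BSA is assessed at Visits 3, 4 and 5. The Schedule of Activities marks BSA at V01, V02, V04 and V05, with nothing at V03. The Visit 3 list in Section 5 has two items: "Collect Tape Stripping" and weighing the tube.

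A child who leaves early has the Visit 5 procedures as an Early Termination visit. These include one ORIA and a record of disposition with reasons. For children who stay, Appendix B has the caregiver complete the ORIA in an eDiary each day, and Section 5 says: "Throughout the study, the participants and caregivers will wear accelerometry/actigraphy devices continuously".

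Section 8.4 handles two other problems differently. For minor application-site pain or stinging in a participant who is uncomfortable going on, the investigator can either keep the child in the study with dosing stopped or withdraw the child. For device discomfort, the investigator "may allow the participant to continue the study without wearing the discomforting device" or withdraw the child.

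Section 9 analyses change in ORIA from Day 2 to Day 15, and accelerometer scratch (ages 2 to 11) from Day 1 to Day 15. The model is a mixed model for repeated measures (MMRM) with treatment, visit, their interaction and the baseline score. Missing values are assumed missing at random. Treatment differences are reported at all post-baseline timepoints. The one sensitivity analysis for the primary endpoints replaces daily values by 3-day averages.

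**The concern.** The rule joins two decisions that can be separated. Stopping the ointment protects the child from it. Withdrawal adds nothing to that protection, but it ends the daily itch diary, device wear and remaining visits for a child who has just worsened.

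The missing values are therefore tied to disease course. The trigger is BSA, which is not in the ORIA model, so missing at random holds only as far as the child's earlier ORIA scores carry the same information. With no post-stop data, the trial cannot check this, and 3-day averaging does not address it. At stake are the treatment differences after the trigger, up to Day 15.

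**Working it through.** **1. The plan's own figure.** Inputs from Section 9: difference 1.0, SD 2.6, two-sided 5%, power 85%, 1:1 allocation. Per arm, n = 2 × (1.960 + 1.036)² × 2.6² / 1.0² = 121.4, so 122 per arm and 244 in total, as stated. The planned 270 less 10% dropout leaves 243.

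**2. Days lost per affected child.** Days lost = 15 − trigger day. The ORIA analysis has 14 days (2 to 15) and the scratch analysis 15 (1 to 15). Visit 4 is Day 8 ± 3.

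| Trigger day | Days lost | Share of 14 ORIA days | Share of 15 scratch days |
|---|---|---|---|
| 5 (earliest Visit 4) | 10 | 71% | 67% |
| 8 (nominal Visit 4) | 7 | 50% | 47% |
| 11 (latest Visit 4) | 4 | 29% | 27% |
| 2 (Visit 3, if BSA were taken there) | 13 | 93% | 87% |

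The Early Termination visit can give back at most one ORIA. Because no BSA is scheduled at Visit 3, Visit 4 is the workable trigger. Read literally as needing both visits, the rule might never fire.

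**3. How many children.** The documents give no number. Entry needs BSA below 40% and mild or moderate disease, and both arms receive an emollient base, so it is probably small. A child who enters just under 40% could still cross the line.

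**4. Effect on the Day 15 difference.** Take the target as outcome whether or not the ointment was stopped. Let p be the share withdrawn in an arm, and e the amount by which their unseen Day 15 score exceeds the MMRM prediction (positive = worse). Then

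bias in estimated benefit = p(crisaborole) × e(crisaborole) − p(vehicle) × e(vehicle).

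All shares and values of e below are assumptions. One percentage point is 1.35 of 135 children per arm.

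| Vehicle / crisaborole share | e | Bias (points) |
|---|---|---|
| 1.5% / 0.5% | +1 to +2.6 in both | −0.010 to −0.026 |
| 3% / 1% | +1 to +2.6 in both | −0.020 to −0.052 |
| 7.5% / 2.5% | +1 to +2.6 in both | −0.050 to −0.130 |
| 3% / 1% | −2.6 in both (better than predicted) | −0.026 + 0.078 = +0.052 |
| 1% / 3% | +2.6 in both | 0.078 − 0.026 = +0.052 |
| 2% / 2% | +2.6 in both | 0 |
| 2% / 2% | +1 vehicle, +2.6 crisaborole | 0.052 − 0.020 = +0.032 |

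The planned difference is 1.0 point. Bias is zero if e is zero (missing at random), or if shares and e are equal across arms. The sign depends on which arm loses more children and on whether later outcomes are worse or better than predicted.

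**5. Power.** With 243 children, power is about 85%. If these withdrawals came on top of the 10% allowance and each such child counted as wholly lost, one extra percentage point gives 240.3 children and 84.6%, and five give 229.5 and 83.0%.

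**The case against.** The strongest case against the point is that it is small, and that post-stop data would not be the same quantity. Such data would be collected off the ointment and possibly on other eczema treatment. Putting them in the primary MMRM moves the target towards outcome regardless of stopping. The plan does not commit to that target. For binary endpoints it counts dropout or prohibited medication as non-response, and for continuous ones it relies on missing at random. This stands. The absence of an exclusion rule in Section 9 does not mean that post-stop values are to be used, so the choice has to be written down.

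Disease spreading past the entry ceiling is also clinically different from minor stinging, so handling the two differently is not an inconsistency. This stands too. Section 8.4 shows only that the protocol already accepts off-treatment follow-up. It leaves that to the investigator's discretion and does not list which assessments continue. A reader might infer that the BSA rule is the one place where leaving is automatic. The documents do not support that, because Section 8.2 also defines a severe adverse event as one that results in withdrawal.

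Withdrawal has a practical benefit as well: it frees the child from the Section 4.1 undertaking not to use other creams or ointments on lesions. A fix that kept the child under that undertaking would be worse for the child. Devices can also provoke a flare (Section 8.4). Both objections shape the fix but do not defeat it.

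Finally, data before the stop and at Early Termination are kept, and early relief, which is a stated goal, is still informed by them. That limits the loss to the later timepoints.

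**Conclusion.** The point holds as a modest, cheap improvement. Section 8.2 ends follow-up where only a dose stop is needed, and a Day 8 trigger costs 7 of 14 ORIA analysis days for that child. This figure is per affected child. It does not describe half of the trial's data.

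A reader might infer that the rule biases the primary result in a known direction, for instance by understating benefit through more withdrawals on vehicle. The documents do not support this. They give no trigger rate for either arm, and other treatment could make later itch better than the MMRM predicts, which reverses the sign. On the assumed values the bias is 0.01 to 0.13 point against a planned 1.0. The top of that range needs a 5-percentage-point imbalance, for which the documents offer no basis. Nor is there a case that power is threatened.

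What remains is avoidable missing data linked to worsening, under an assumption that the trial could not check, plus a trigger visit that the schedule does not support.

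**What to change.** Keep the dose stop. In Section 8.2, replace the withdrawal clause with wording to this effect: *the child will stop the ointment, is released from the restriction on other AD treatment, and will by default continue the daily ORIA, device wear where tolerated, and the remaining visits to Day 15, unless the family declines or the investigator judges it unsafe.*

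In addition:
- Name the visit or visits at which the rule applies. Either add BSA to Visit 3 or limit the rule to Visit 4.
- Record the date and reason of the dose stop and any other AD treatment started.
- State in Section 9, before unblinding, whether post-stop data enter the primary MMRM. Run the alternative, with or without data after other AD treatment begins, as a supportive analysis.

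Cost: a protocol amendment with IRB approval (Section 11.2) and possibly a consent revision, one added field, and one supportive analysis. Disposition reasons (Visit 5 list) and concomitant medications (Section 10.2) are already collected. A few families continue the diary and devices for about 4 to 10 more days, and some of the data will reflect other treatment. The sample size does not change.

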conducted to assess frequency of events, severity, seriousness, and relatedness to determine any potential trending study related items that may indicate a potential safety concern.

The data for adverse events (observed by study staff or spontaneously reported by caregivers) will be aggregated using descriptive statistics. Overlap of adverse events will be recorded.

Caregiver reported treatment-related adverse events will be recorded using MedDRA Version 24.1.

Severity of adverse events will be categorized as follows: Mild-Symptom(s) barely noticeable with no reported participant discomfort; Moderate- Symptom(s) reported as uncomfortable; Severe- Symptom(s) causing severe discomfort resulting in participant withdrawal. Relatedness of reported events will be categorized as follows: Unrelated- The event deemed to be clearly not study related; Possibly related- The event is temporally aligned with study activities but possibly may be due to another circumstance; Related- The event is temporally aligned to study activities with no alternative causes present.

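### Relatedness is graded against study activities as a whole, and the only MedDRA rule covers a treatment-related category that this scale does not contain and that is narrower than the adverse events being aggregated

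*Combined protocol and SAP*

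**What the plan says.** Section 8.2 sets out collection, coding and grading of adverse events.

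- **What is aggregated:** "The data for adverse events (observed by study staff or spontaneously reported by caregivers) will be aggregated using descriptive statistics". Both reporters are included.
- **What is coded:** "Caregiver reported treatment-related adverse events will be recorded using MedDRA Version 24.1". No other coding rule appears in the protocol.
- **How relatedness is graded:** three levels. The lowest reads "Unrelated- The event deemed to be clearly not study related". The middle level asks for a match in time with what happens in the study, while leaving room for some other cause. The highest reads "Related- The event is temporally aligned to study activities with no alternative causes present". All three refer to the study or its activities, and none refers to the ointment.
- **What staff look for at visits:** "study staff will assess the level of skin irritation and participant reported discomfort (or AD flare up) from both the wearing of devices". The ointment is covered in the same sentence. Tape stripping is not named.

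Sections 8.2 and 8.3 add a monthly review of blinded events covering frequency, severity, seriousness and relatedness. Section 9 plans a summary of AEs and RRIs in one line, with no table layout, coding level or split by source.

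**The concern.** Two rules in the same section do not fit together. The coding rule selects events by a judgement, treatment-related, that the grading scale does not produce. Two coders working from the protocol could therefore select different events. The rule is also silent on events that staff find and on events judged unrelated, although both belong to the adverse events to be summarised.

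Separately, the study exposes each child to three possible causes of a skin reaction: ointment, up to four wearable devices, and tape stripping. A single grade against study activities does not record which one is suspected. The monthly review is meant to detect trends and works on blinded data, so it cannot fall back on comparing the arms. If skin events rise, the plan specifies nothing that would point to the source. The source matters because Section 8.4 links device reactions and ointment reactions to different responses.

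**Working it through.** The plan states no figure on this point, so the check sets its provisions side by side.

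**1. Scope of coding against scope of aggregation (Section 8.2)**

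| Event type | Aggregated? | Coding rule stated? |
|---|---|---|
| Caregiver-reported, treatment-related | Yes | Yes, but the category is undefined |
| Caregiver-reported, other | Yes | No |
| Staff-observed, any relatedness | Yes | No |

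The adverse event definition in Section 8.1 includes events regardless of relatedness, so the last two rows are part of the adverse event population.

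**2. Can treatment-related be derived from the scale?** No. An event graded Related or Possibly related may be due to ointment, device or tape. The scale gives no rule for moving from study-related to treatment-related.

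**3. Do the sources overlap?** (Sections 5, 7 and 8.4, Schedule of Activities, tape-stripping guide)

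| Source | Skin effects named in Section 8.4 | When | Where |
|---|---|---|---|
| Devices | "possible skin irritation or reaction, such as an AD flare-up in children with the skin condition" | V01 to V05 | Wrists; also ankles under 2 years |
| Tape strips | "mild discomfort and potentially superficial surface reddening of the skin at the location of the tape" | V01, V03, V05 | Lesional site inside the area to be treated; non-lesional site at V01 only |
| Crisaborole | Pain, burning or stinging, swelling, erythema, hypersensitivity | From V02 | Active lesions, with stated exceptions |
| Vehicle | Almost the same list | From V02 | As crisaborole |

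Symptoms overlap for all the sources. Site overlaps for ointment and the lesional tape strip. Timing can overlap too: the second strip is on Day 2, one day after first application, and Section 8.4 describes ointment stinging as lasting one to two days. Redness at that site could be graded only for its relation to the study.

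**4. Events before exposure.** Section 5 places random assignment, device issue and the first tape strip at V01 (Day -7). Ointment is dispensed at V02 (Day 1). Adverse event monitoring covers this interval. Device and tape reactions in that week can therefore be graded study-related and counted by arm before any ointment has been applied. No split is specified.

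**5. Effect on the comparison between arms.** Devices and tape strips are scheduled alike in both arms. Suppose they cause a reaction with probability b in each arm, independently of ointment reactions with probabilities p1 and p0. The proportion with any reaction is 1 − (1 − p)(1 − b), and the difference between arms is (p1 − p0)(1 − b). The documents give no rates, so those below are assumptions: p1 = 6%, p0 = 3%, a difference of 3.0 points.

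- b = 5%: 1 − 0.94 × 0.95 = 10.7% and 1 − 0.97 × 0.95 = 7.85%, a difference of 2.85 points.
- b = 10%: 1 − 0.94 × 0.90 = 15.4% and 1 − 0.97 × 0.90 = 12.7%, a difference of 2.7 points.

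Shared reactions add background to both arms. They do not favour either arm, and on these assumptions the absolute difference changes little.

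**The case against.** Several counter-arguments are sound and limit the point.

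- **Staff-observed events are not left out.** A reader might infer from the MedDRA sentence that they are missing from the tables. Section 8.2 expressly aggregates them and also keeps a list of all identified safety events. The sentence does not exclude other coding; it is silent.
- **The sources are not inseparable.** A reader might infer that ointment and device reactions cannot be told apart. Staff assess both at visits, the dosing record shows where ointment went, the tape site is documented and photographed, and device positions are fixed. What is missing is a specified record of suspected source, and tape stripping is not in the visit assessment.
- **Randomisation protects the comparison.** A reader might infer that device and tape reactions bias the arm difference. They are scheduled alike in both arms, so they add noise without favouring either. The plan also does not restrict its summary to study-related events.
- **Tape reactions may be few.** Section 8.4 calls the risk minimal and says reddening is typically reported after 50 to 60 strips, against about 20 per sample here.
- **The strict wording of Related loses no events.** A skin event with another possible cause moves to Possibly related. Loosening Related would blur the two levels, so that definition need not change.
- **The adverse event form is not in the document.** Section 10 refers data handling to the IRB application, and Section 10.2 aligns the data dictionary to CDISC and sponsor standards. A source field may exist there.

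The mismatch in Section 8.2 remains after all of these. Comparing arms also cannot identify reactions to the shared ointment base or the source of an individual event. The monthly review's other inputs (frequency, severity, seriousness) do not supply source.

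**Conclusion.** The point holds as a gap in specification. The only coding rule is narrower than the adverse events to be summarised and rests on a category that the relatedness scale does not contain. Relatedness is graded against the study as a whole, although ointment, device and tape reactions overlap in symptoms and partly in site. Events in the week between randomisation and first ointment are not set apart.

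The consequence is modest: background noise in the safety summary, and weak attribution in the blinded monthly review and for reactions to the shared base. The crisaborole-versus-vehicle comparison stays unbiased, no adverse event is shown to be lost, and no efficacy analysis is affected. The size cannot be given from the documents because they state no reaction rates. The conclusion assumes that the protocol text governs and that no unseen form or coding convention already supplies what is missing. It is worth correcting because the correction is cheap.

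**What to change.** In Section 8.2:

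1. Replace the MedDRA sentence with a rule that codes every adverse event, whoever reported it and whatever its relatedness.
2. Keep the three relatedness levels, but record a grade separately for study ointment, wearable device and tape stripping. Define treatment-related, if the term is kept, from the ointment grade.
3. Name tape stripping alongside devices and ointment in the visit assessment.

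In Section 9, state that adverse events will be tabulated by arm, with events before first application shown separately from those after it, and with relatedness by source.

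If the adverse event form already holds a source field, a cross-reference is enough for item 2. Otherwise the cost is a few extra fields on the form and modest additional coding work. No visit, procedure or efficacy analysis changes.
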